5.4 SECONDARY ENDPOINTS ANALYSES

The continuous secondary efficacy endpoints will be analyzed using the same primary statistical model as for the primary endpoints. All time-to-event endpoints will be analyzed with a stratified log-rank test using the primary analysis stratification factors. Within each time-to-event endpoint, the hazard ratio (HR) for recurrence will be estimated using a stratified Cox proportional hazards model, and the 95% CI for the HR will be provided. Stratification factor(s) may be removed from the stratified analyses if there is risk of non-convergence or sparse strata (*in the case of non-convergence, stratification factors will be removed in the order of the smallest number of observations in any cell caused by that stratification factor*).

5.4.1 **Key/Confirmatory Secondary Endpoints**

The key secondary endpoints are:

- *Annualized rate of change in mean cerebral fibrillar amyloid accumulation using florbetapir PET from a predefined ROI*
 - *SUVrs will be derived from florbetapir PET images using a composite region of interest (including frontal, temporal, parietal, and cingulate cortices) with a subcortical white matter reference region*
- Time to progression from preclinical AD to MCI due to AD or from preclinical AD to dementia due to AD
- Annualized rate of change in the CDR Scale-Sum of Boxes
- Time to progression to non-zero in CDR global score
- Annualized rate of change in a measure of overall neurocognitive functioning: RBANS total score

Time to progression is calculated from the time at baseline, which is the last record on or prior to the first baseline reference date; the baseline reference date is either the first exposure date or the randomization date if the first exposure date is missing.

A gatekeeping strategy will be used for testing hypotheses of the key secondary outcomes using the graph-based type I error approach described in Section 3.1, the key secondary outcomes will be tested only if both the primary endpoints are statistically significant. All the tests will be done based on a two-sided $\alpha=0.05$. The tests in the key secondary outcomes will be done in sequential order specified in the following:

1. Annualized rate of change in mean fibrillar amyloid accumulation in a composite region (including frontal, temporal, parietal, and cingulate cortices) with a subcortical white matter reference region using florbetapir PET
2. Log-rank analysis of time to progression from preclinical AD to MCI due to AD or from preclinical AD to dementia due to AD
3. RCRM analysis of CDR Scale-Sum of Boxes
4. Log-rank analysis of time to progression to non-zero in CDR global score
5. RCRM analysis of RBANS total score

At initial study readout if the study is positive (at least one of the primary endpoints is statistically significant), the Sponsor will analyze all available data from the key secondary biomarker endpoint: annualized rate of change in mean cerebral fibrillar amyloid accumulation in a composite region (including frontal, temporal, parietal, and cingulate cortices) with a subcortical white matter reference region using florbetapir PET. If the study is negative (neither of the primary endpoints are statistically significant), the Sponsor will analyze at least the baseline and last-available (in time) data from the florbetapir PET endpoint at the initial study readout, which is at the *primary analysis*.

5.4.2 Supportive Secondary Endpoints

The supportive secondary biomarker endpoints include:

- *Annualized rate of change in regional cerebral metabolic rate of glucose (CMRgl) using FDG-PET in a predefined ROI*
 - *Annualized rate of change in regional (CMRgl) will be derived from FDG PET images using an empirically predefined statistical ROI (sROI) known to be preferentially affected by CMRgl decline in persons with AD (Chen et al. 2010; Van Dyck et al. 2019)*
- *Annualized rate of change in volumetric measurements using MRI*
 - *Regions will include the whole brain, bilateral hippocampus, and bilateral ventricles*
- *Annualized rate of change in CSF tTau and pTau biomarkers*

Similar to the approach from the key secondary biomarker efficacy endpoint, the Sponsor will analyze all available data on the FDG-PET and volumetric MRI data if the study is positive. Otherwise, the Sponsor will analyze at least the baseline and last-available (in time) data on FDG-PET and volumetric MRI at the initial study readout.

5.5 EXPLORATORY ENDPOINTS ANALYSIS

Exploratory outcome measures are listed below. The continuous endpoints will be analyzed using the RCRM from the primary analysis and/or using an MMRM; the correlation analysis among outcomes will be modeled using a Spearman correlation estimation. The “mutation non-carriers treated with placebo” in this section is defined as all randomized mutation non-carriers that received at least 1 dose of study drug.

5.5.1 Clinical

Changes from baseline over time in the following cognitive measures:

- Trail Making Test ([Armitage 1946](#))
- MMSE ([Folstein et al. 1975](#))
- RBANS Index Scores ([Randolph 1998](#))
- Scores from each of the components of the API ADAD Composite Cognitive Test Battery
- Preclinical Alzheimer Cognitive Composite (PACC; [Donohue et al. 2014](#)) modified for the API ADAD trial; PACC is calculated as the standardized sum of MMSE, RBANS story recall, RBANS coding, and FCSRT total score (sum of 3 free and cued recall trials)
- Clinical endpoints not examined in secondary outcome measures
- Changes in the Neuropsychiatric Inventory (NPI) total score, items, and factors ([Cummings et al. 1994; 1997](#))

- Changes in the Geriatric Depression Scale (GDS) total score ([Sheikh and Yesavage 1986](#))
- Changes in Functional Assessment Staging of Alzheimer's Disease (FAST) total score ([Sclan and Reisberg 1992](#))
- Changes in Subjective Memory Checklist ([Acosta-Baena et al. 2011](#))

5.5.2 Fluid Biomarkers

- CSF levels of A β ₁₋₄₂ and A β ₁₋₄₀
- Changes in other blood and CSF measures such as neurofilament light (NfL) and plasma tau markers

5.5.3 Imaging Biomarkers

- Analysis of other *regional or global measures* not selected in secondary outcome measures. *See the biomarker analysis plan for more details.*
- Other imaging outcome measures and analytic methods, alone, or in conjunction with other imaging modalities not explored in secondary outcome measures
- Change in tau burden over time, as measured by *Genentech Tau Probe 1 (GTP1)* PET in an optional substudy (GN28352-1/BN40199). *See Section 5.8 for analysis details.*

5.5.4 Other Endpoints

See the biomarker analysis plan for more details on the following endpoints:

- Changes in primary, secondary, and exploratory outcomes in mutation non-carriers treated with placebo
- Comparisons of clinical and biomarker outcomes between carriers treated with placebo and non-carriers
- Changes in primary, secondary, and exploratory outcomes in carriers and non-carriers as functions of the APOE genotype and other genetic variations
- Short-term changes in imaging measures as functions of initiation (e.g., baseline to 12 weeks)
- Analyses of outcome measures in relation to one another and in relation to baseline characteristics

5.6 SAFETY ANALYSES

All safety analyses of Study Period A will be performed in the safety-evaluable population (see Section 4 for definition).

As the study participants are considered treatment-exposed during the 16-week (approximately 5 half-lives) follow-up period, adverse events reported within 16 weeks after the last dose of study drug administered in Study Period A will be included in the safety analyses from Study Period A (contrary to the description in the protocol stating they will be summarized separately). At the end of Study Period B, safety analyses on

Study Period A will be refreshed (*due to the additional 16-week safety follow-up data accrued in Period A after the primary analysis*) and reported in the final CSR.

Adverse events reported within 16 weeks after the last dose of study drug administered in Study Period B will be included in the safety analyses on Study Period B.

Safety analyses of Study Period B and/or of the potential OLE data are summarized in Section 5.10.2.

Safety will be assessed through summaries of exposure to study treatment, adverse events, changes in laboratory test results, MRI findings, changes in vital signs and ECGs, and changes in suicidality assessment.

Study treatment exposure (such as treatment duration, total dose received, and dose modifications) will be summarized with descriptive statistics.

All verbatim adverse event terms will be mapped to MedDRA thesaurus terms, and adverse event severity will be graded according to National Cancer Institute Common Terminology Criteria for Adverse Events (NCI CTCAE), v4.0. All adverse events, serious adverse events, adverse events leading to death, adverse events of special interest, and adverse events leading to study treatment discontinuation that occur on or after the first dose of study treatment (i.e., treatment-emergent adverse events) will be summarized. All adverse events will be summarized by severity and by relationship to study drug. For events of varying severity, the highest grade will be used in the summaries.

Relevant laboratory, vital signs (pulse rate, respiratory rate, blood pressure, pulse oximetry, and temperature), and ECG data will be displayed by time, with grades identified where appropriate. Additionally, a shift table of selected laboratory tests will be used to summarize the baseline and maximum post-baseline severity grade.

Changes in vital signs and ECGs will be summarized. Proportion of participants with suicidal ideation or behavior, as reported in the suicidality assessment, will be analyzed by treatment groups.

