4.5.7 Follow-Up Assessments

Participants who complete the treatment phase of the study will return to the clinic for an end of treatment visit 4 weeks after the last dose (ET-A or ET-B). Following the completion of Study Period A, participants will be offered the opportunity to continue to receive study drug until the results of the study are known and post-trial access to crenezumab is started (via an OLE or other program) or development of crenezumab is discontinued (see Section [4.5.8](#)). For those participants that do not choose to continue study drug in Study Period B, a final safety follow-up visit will occur 16 weeks after the last dose (see [Appendix 2](#) or [Appendix 4](#)).

Any adverse event (including a clinically significant laboratory abnormality) that is unresolved at the end of the study will continue to be followed until the event is resolved or stabilized, the participant is lost to follow up, or it has been determined that the study treatment or participation is not the cause of the event. Every effort should be made to follow all serious adverse events considered to be related to study drug or study procedures until a final outcome can be reported.

Please see the study flowchart provided in [Appendix 2](#) or [Appendix 4](#) for specified follow-up assessments.

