4.10.4.1 Adverse Events

Adverse events will be recorded from the time informed consent is given until 16 weeks following the last administration of any investigational product, or a participant completes the study or discontinues prematurely, whichever occurs last (see Section [5.2.1](#) for details).

As the study participants are considered treatment-exposed during the 16-week (approximately 5 half-lives) follow-up period, adverse events reported within 16 weeks after the last dose of study drug administered in Study Period A will be included in the safety analyses from Study Period A. During Study Period B, safety data from Study Period A will be refreshed and reported in the final CSR. Verbatim descriptions of adverse events will be coded and analyzed using appropriate thesaurus terms. A treatment-emergent adverse event is defined as any adverse event reported on or after the first dose of study drug.

Adverse events occurring during Study Period B, up through 16 weeks after the last dose, will be summarized in the final CSR.

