Appendix 2 (SC Dosing) (Week 106–End of Study Period A) (cont.)

AD = Alzheimer's disease; ADA = anti-drug antibody; ADAD = autosomal-dominant Alzheimer's disease; API = Alzheimer's Prevention Initiative; CDR = Clinical Dementia Rating; CERAD = Consortium to Establish a Registry for Alzheimer's Disease; Comp = completion; CSF = cerebrospinal fluid; d = day; ET = early termination; FAST = Functional Assessment Staging of Alzheimer's Disease; FDG = fluorodeoxyglucose; GDS = Geriatric Depression Scale; LP = lumbar puncture; MCI = mild cognitive impairment; MMSE = Mini-Mental State Examination; MRI = magnetic resonance imaging; NPI = Neuropsychiatric Inventory; PD = pharmacodynamic; PET = positron emission tomography; PK = pharmacokinetic; Q2W = every 2 weeks; SMC = Subjective Memory Checklist; SPCQ = Study Partner Characterization Questionnaire; W = week.

Note: On treatment days, all assessments should be performed prior to dosing unless otherwise noted.

- ^a Participants who discontinue from study drug treatment (early discontinuation) will not receive further doses of study drug, but should be asked to stay in the study for subsequent safety, cognitive, and biomarker assessments at complex visits, including at Weeks 24, 36, 52, 76, 104, 128, 156, 180, 208, 232, 260, and every 24–28 weeks thereafter until the study ends. In addition, the suicidality assessment, review of concomitant medications and adverse events should be collected at Weeks 12, 64, 92, 116, 144, 168, 196, 220, 248, and every 24–28 weeks until the study ends; these assessments may be completed by telephone (but it is preferred they be completed in person). If a phone visit is completed during these weeks, vital signs assessments may be omitted.
- ^b If a participant discontinues from the study (ET) or discontinues from study drug treatment and elects to no longer stay in the study, ET Visit A should be completed if the last visit occurred more than 12 weeks after functional, behavioral and cognitive assessments were performed;
- ^c If a participant discontinues from the study (ET) or discontinues from study drug treatment and elects to no longer stay in the study, ET Visit B should be performed if the last visit occurred within 12 weeks of functional, behavioral, and cognitive assessments.
- ^d Safety follow-up at 16 weeks is only applicable for those participants that do not consent to the continued access study.
- ^e Weight should be obtained at all weeks marked on the study flowchart.

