AD = Alzheimer's disease; ADA = anti-drug antibody; ADAD = autosomal-dominant Alzheimer's disease; API = Alzheimer's Prevention Initiative; CDR = Clinical Dementia Rating; CERAD = Consortium to Establish a Registry for Alzheimer's Disease; CSF = cerebrospinal fluid; d = day; ET = early termination; FAST = Functional Assessment Staging of Alzheimer's Disease; FDG = fluorodeoxyglucose; GDS = Geriatric Depression Scale; LP = lumbar puncture; MCI = mild cognitive impairment; MMSE = Mini-Mental State Examination; MRI = magnetic resonance imaging; NPI = Neuropsychiatric Inventory; PD = pharmacodynamic; PET = positron emission tomography; PK = pharmacokinetic; Q4W = every 4 weeks; SMC = Subjective Memory Checklist; SPCQ = Study Partner Characterization Questionnaire; W = week.

Appendix 4
(IV Dosing) Study Flowchart (Week 108–End of Study Period A) (cont.)

Note: On treatment days, all assessments should be performed prior to dosing unless otherwise noted.

- ^a Participants who discontinue from study drug treatment (early discontinuation) will not receive further doses of study drug, but should be asked to stay in the study for subsequent safety, cognitive, and biomarker assessments at complex visits, including at Weeks 24, 36, 52, 76, 104, 128, 156, 180, 208, 232, 260, and every 24–28 weeks thereafter until the study ends. In addition, the suicidality assessment, review of concomitant medications and adverse events should be collected at Weeks 12, 64, 92, 116, 144, 168, 196, 220, 248, and every 24–28 weeks until the study ends; these assessments may be completed by telephone (but it is preferred they be completed in person). If a phone visit is completed during these weeks, vital signs assessments may be omitted.
- ^b If a participant discontinues from the study (ET) or discontinues from study drug treatment and elects to no longer stay in the study, ET Visit A should be completed if the last visit occurred more than 12 weeks after functional, behavioral and cognitive assessments were performed.
- ^c If a participant discontinues from the study (ET) or discontinues from study drug treatment and elects to no longer stay in the study, ET Visit B should be performed if the last visit occurred within 12 weeks of functional, behavioral, and cognitive assessments.
- ^d Safety follow-up 16 weeks after last dose is only applicable to participants that do not consent to participate in the continued access study.

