Single 12-Lead ECG ⁱ				x		x	x	x
Physical and neurologic examinations ^j				x		x		x
Serum chemistry and hematology ^{k,l}				x		x		x
MRI ^m						x		
Optional CSF ^{n,p}						x		
Optional Tau-PET ^{o,p}						x		
Amyloid-PET ^p						x		
Evaluate criteria for MCI/AD			x	x	x	x	x	
GDS ^{q,r}			x	x	x	x	x	

Appendix 5
Study Flow Chart for Study Period B: SC Dosing (cont.)

	W1 and Every 2 Weeks Thereafter ^a	W13	W25	W53	W77	W105	W157 and Every 52 Weeks Thereafter	ET/SFU Last Dose + 16 W ^b
Assessment window	(±7d)	(±7d)	(±7d)	(±7d)	(±7d)	(±7d)	(±7d)	(±7d)
SMC ^{q,r}			x	x	x	x	x	
API ADAD Cognitive Composite Battery ^s			x	x	x	x	x	
FCSRT ^s			x	x	x	x	x	
Trail Making Tests A and B ^s			x	x	x	x	x	
RBANS ^s			x	x	x	x	x	
SPCQ ^{u,r,t}			x	x	x	x	x	
CDR ^{q,r,t}			x	x	x	x	x	
FAST ^{r,t}			x	x	x	x	x	
NPI ^{r,t}			x	x	x	x	x	
Suicidality assessment ^{q,r}			x	x	x	x	x	
Study drug administration ^{v,w,x}	x	x	x	x	x	x	x	
Concomitant medication review ^r	x	x	x	x	x	x	x	x
Adverse event review ^r	x	x	x	x	x	x	x	x

AD = Alzheimer's disease; ADA = anti-drug antibody; ADAD = autosomal-dominant Alzheimer's disease; CDR = Clinical Dementia Rating; CERAD = Consortium to Establish a Registry for Alzheimer's Disease; CSF = cerebrospinal fluid; d = day; ET = early termination; FAST = Functional Assessment Staging of Alzheimer's Disease; FCSRT = Free and Cued Selective Reminding Test; GDS = Geriatric Depression Scale; MCI = mild cognitive impairment; MMSE = Mini-Mental State Examination; MRI = magnetic resonance imaging; NPI = Neuropsychiatric Inventory; PD = pharmacodynamic; PET = positron emission tomography; PK = pharmacokinetic; RBANS = Repeatable Battery for the Assessment of Neuropsychological Status; SFU = safety follow-up; SMC = Subjective Memory Checklist; SPCQ = Study Partner Characterization Questionnaire; W = week.

Appendix 5
Study Flow Chart for Study Period B: SC Dosing (cont.)

- ^a Week 1 is the first dose in Study Period B and may occur on the same day as the final ET-A or ET-B visit in Study Period A after all ET assessments are completed and the investigator deems dosing is appropriate.
- ^b Early termination visit/SFU visit, occurring when someone terminates prior to the end of the Study Period B, should be done 16 weeks after the last dose of study drug. Participants who continue crenezumab treatment after the end of Study Period B will not have a “last dose + 16 weeks visit”.

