The study duration for individual participants will be at least approximately 284 weeks, including an 8-week screening period, a double-blind treatment period of at least 260 weeks in length, a 4-week final dose visit, and a final safety follow-up visit 16 weeks after the last dose of study drug (crenezumab or placebo) that will allow for clinical follow-up after treatment discontinuation for participants who do not continue with study drug beyond the end of Study Period A or who terminate study drug early. Per protocol, all participants are assessed with clinical cognitive measures, magnetic resonance imaging (MRI), fluorodeoxyglucose (FDG) positron emission tomography (PET), amyloid PET, and blood-based biomarkers per the schedule of activities. Cerebrospinal fluid (CSF) collection is optional and tau PET is collected in an optional substudy.

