1.2.2 Study Period B

Following the completion of Study Period A, participants will be offered the opportunity to continue to receive study drug until the results of the study are known. This is termed Study Period B. All *PSEN1* mutation carriers will be provided crenezumab in Study Period B regardless of treatment allocation during Study Period A, and all non-carriers will continue on placebo. Treatment allocation for both Study Periods A and B will remain blinded. Study Period B may last up to approximately 12 months depending on when participants enter Study Period B. See [Figure 2](#).

[figure not shown]
*After the primary efficacy results from Study Period A are available, the Sponsor may extend Study Period B, or initiate an OLE study for *PSEN1* E280A autosomal-dominant mutation carriers, or development of crenezumab may be discontinued.*

Figure 1 Study Design

RCT = randomized, controlled trial.

Figure 2 Study Schematic

ETA/ETB = end of treatment visit A or end of treatment visit B; OLE = open-label extension; SFU = safety follow-up; W = week.

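### The Period A adverse-event window is not cut at the first Period B dose, so up to about 12 weeks of placebo carriers' first crenezumab exposure falls under placebo in Period A

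*SAP*

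**What the plan says.** **Inclusion rule.** SAP 5.6 says that "adverse events reported within 16 weeks after the last dose of study drug administered in Study Period A will be included" in the Period A safety analyses. Protocol 4.10.4.1 has the same sentence. Neither mentions the first Period B dose as an end point, and the treatment-emergent definition in SAP 5.6.2 has no end date.

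**Period B reporting.** Protocol 4.10.4.1 adds: "Adverse events occurring during Study Period B, up through 16 weeks after the last dose, will be summarized in the final CSR". SAP 5.6 has a matching Period B sentence. Neither excludes events already counted in Period A.

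**Timing.** Protocol 4.5.7 says that participants who finish treatment "will return to the clinic for an end of treatment visit 4 weeks after the last dose". Footnote a of protocol Appendices 5 and 6 says: "Week 1 is the first dose in Study Period B and may occur on the same day as the final ET-A or ET-B visit".

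**Treatment in Period B.** SAP 1.2.2 says that all "mutation carriers will be provided crenezumab in Study Period B regardless of treatment allocation during Study Period A".

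**Grouping.** Protocol 3.6 groups safety analyses by the drug actually received. SAP 4 introduces the safety-evaluable set as a Study Period A population and moves placebo participants with more than 2 crenezumab doses to the crenezumab arm. SAP 5.10 defines a separate Period B safety population.

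**The 16-week visit.** SAP 1.2.1 describes this visit as being for "participants who do not continue with study drug beyond the end of Study Period A or who terminate study drug early". Footnote d of protocol Appendix 2 says: "Safety follow-up at 16 weeks is only applicable for those participants that do not consent to the continued access study". Footnote d of Appendix 4 says the same for IV dosing.

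**The concern.** A placebo carrier who enters Period B can receive a first dose of crenezumab about 4 weeks into a 16-week window that still belongs to Period A. Followed literally, the rule places adverse events from the first weeks on crenezumab in the Period A placebo column. The same events are also reported under crenezumab in Period B.

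The reason given for the window is that participants remain exposed for about 5 half-lives. That does not apply to a placebo carrier, who has no Period A crenezumab to wash out. SAP 5.6.1 ends treatment duration at Period A treatment completion, so the event window runs on after the exposure summary has stopped.

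What is at stake is the Period A contrast for early-onset events. Protocol 3.5.4 defines injection and infusion reactions as any adverse event during a dose or in the following 24 hours. SAP Table 1 lists their incidence as a safety endpoint, and SAP 5.6.2 tabulates them by treatment group. Reactions to first crenezumab doses counted under placebo would narrow the crenezumab-placebo difference. ARIA found on scheduled scans is little affected, because the scheduled Period B MRI is at Week 105.

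**Working it through.** **Reproducing the plan's timeline.** SAP 1.2.1 gives a minimum individual duration of about 284 weeks.
- 8 (screening) + 260 (treatment) + 16 (follow-up) = 284, which matches.
- Adding the 4-week visit separately gives 8 + 260 + 4 + 16 = 288, which does not match.
- The 4-week visit therefore lies inside the 16-week window.
- The window also agrees with its description as about 5 half-lives: 112 days divided by the half-life of 17 to 26 days (protocol 1.2.2.2) is 6.6 to 4.3 half-lives.

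**Overlap.** Overlap = 16 weeks minus the time from last Period A dose to first Period B dose.
- Period B starts on the day of the end-of-treatment visit: 16 − 4 = 12 weeks (84 of 112 days, 75% of the window).
- With the ±7-day window for that visit (protocol Appendices 2 and 4): 11 to 13 weeks.
- A later Period B start shortens the overlap.
- In 12 weeks, 3 IV doses (days 28, 56 and 84 after the last Period A dose) or 6 SC doses (days 28 to 98, every 14 days) fit before day 112. Counting day 112 itself gives 4 or 7.

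**Share of the Period A window.** 12/(260 + 16) = 4.3% at the minimum duration. For a participant treated to Week 416, 12/(416 + 16) = 2.8%.

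**Person-years.** The number of placebo carriers is an assumption: 84, from the simulation in SAP Appendix 2 that mimics this study. The 63 applies the planning dropout of 25% to it (84 × 0.75).

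| Placebo carriers starting Period B on the visit day | 11 weeks | 12 weeks | 13 weeks |
|---|---|---|---|
| 84 | 84 × 11/52 = 17.8 | 84 × 12/52 = 19.4 | 84 × 13/52 = 21.0 |
| 63 | 63 × 11/52 = 13.3 | 63 × 12/52 = 14.5 | 63 × 13/52 = 15.8 |

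**Effect of one event.** On a per-participant incidence, only a placebo carrier with no earlier event of that type changes the figure.
- Among placebo carriers: 1/84 = 1.2 percentage points.
- Pooled with non-carriers: 252 recruited (protocol 3.2) − 168 carriers = 84 non-carriers, an inference, so 1/(84 + 84) = 0.6 points.

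**After the change proposed below.** The Period A tail for a participant who starts Period B on the visit day is about 4 weeks (3 to 5), and the overlap is zero.

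**The case against.** The strongest reply is that the sponsor meant something narrower. SAP 5.6 explains the refresh of the Period A tables by follow-up data accrued in Period A, and events after a first Period B dose do not obviously accrue there. The inclusion sentence rests on a follow-up period, and the 16-week visit is reserved for people who do not continue or who stop early. This stands as evidence of intent. It does not settle the matter: those passages limit a visit or explain a refresh, whereas the inclusion rule covers every participant, and adverse events are collected throughout Period B. A programmer following the sentence as written would include them.

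The reply on size also stands. The safety comparisons are descriptive, the person-year figures are ceilings, and the documents give no crenezumab excess in reactions from which a dilution could be calculated.

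A reader might infer two stronger things.
- **Wholesale regrouping.** The third Period B dose comes 28 days (SC) or 56 days (IV) after the first, inside an 84-day overlap. One could therefore think that rollover placebo carriers pass the 2-dose threshold and take years of placebo events into the crenezumab arm. The documents do not support this. SAP 4 defines the set for Study Period A, and SAP 5.10 has its own Period B population, so the clause most naturally counts Period A doses. It should say so.
- **Inflated totals.** An event shown in two period-specific tables is not counted twice within either, and no planned table is identified that adds them. The fault is attribution in the Period A table.

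**Conclusion.** The concern holds as a gap in a stated rule. As written, up to about 12 weeks (11 to 13) of rollover placebo carriers' first crenezumab exposure lies inside the Period A event window. Those events are shown under placebo there and under crenezumab in Period B, contrary to protocol 3.6. The sponsor may not have intended this, but the text does not exclude it.

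The effect is small: a ceiling of 19.4 person-years if all of an assumed 84 placebo carriers start Period B on the visit day, or 14.5 if 63 do. Actual rollover numbers and start dates are not given. It bears mainly on injection and infusion reactions and other early-onset events. No event is lost from the report, no efficacy result is touched, and no change in any event rate can be estimated from the documents. It is worth correcting because followed literally the rule gives a wrong attribution, and the correction is short.

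**What to change.** In SAP 5.6 and protocol 4.10.4.1, end the Period A adverse-event window at the earlier of 16 weeks after the last Period A dose or the first Period B dose, in both arms. Report later events in Period B. In SAP 4, state that the 2-dose clause counts only crenezumab doses received in Period A.

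A minor wording alignment belongs in the same edit. The safety-evaluable and tau-safety-evaluable rows of SAP 4 send every participant with no more than 2 crenezumab doses to placebo. Read literally, that would move crenezumab-randomised participants who stop after 1 or 2 doses, contrary to protocol 3.6. The pharmacokinetic-evaluable set and the Period B safety population apply the threshold to placebo participants only, so this is probably a drafting slip. The two rows should be limited in the same way. The number affected is not stated.

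The cost is SAP and protocol wording and minor reprogramming, with no new data. The Period A tail becomes up to about 12 weeks shorter for rollovers than for non-rollovers, in both arms. Events in crenezumab rollovers in those weeks, including any carry-over from Period A dosing, would be reported in Period B only.
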